8.3 Exploratory Outcomes

For all *other outcomes*, we will measure the following:

- 3-D Confusion Assessment Method³⁴
 - Measurement: proportion of patients who develop delirium according to 3-D Confusion Assessment Method, a clinically validated algorithm of delirium diagnosis, on any of the postoperative days 1 to 3.
 - Range: 0-100%
- Postoperative Quality of Recovery Scale³⁵
 - Measurement: a clinically validated scale that includes physiologic, nociceptive, functional, cognitive, emotional recovery domains assessed as well as overall patient perspective on postoperative day 3.
 - Range: 40-200 (higher values indicate better recovery)
- Comprehensive complication index³⁶
 - Measurement: a composite complication grading system by Clavien-Dindo Classification after an intervention
 - Range: 0-100 (higher values indicate more severe complications)
- Length of stay (time to readiness to discharge)
 - Measurement: number of hospital days from surgery until a patient becomes medically stable for discharge based on clinical notes
 - Range: ≥ 1 day
- 30-day readmission from all causes
 - Measurement: proportion of patients who were readmitted within 30 days of surgery
 - Range: 0-100%
- 30-day mortality from all causes
 - Measurement: proportion of patients who died within 30 days of surgery
 - Range: 0-100%
- 90-day mortality from all causes

- Measurement: proportion of patients who died within 90 days of surgery
 - Range: 0-100%
- Change in PROMIS-CAT score in participation in social roles/activities (4 questions)
 - Measurement: self-reported measure of participation in social roles/activities
 - Range: 0-100 (higher values indicate higher participation)
- Change in PROMIS-CAT score in Anxiety (4 questions)
 - Measurement: self-reported measure of anxiety
 - Range: 0-100 (higher values indicate more anxiety)
- Change in PROMIS-CAT score in Depression (4 questions)
 - Measurement: self-reported measure of depression
 - Range: 0-100 (higher values indicate more depression)
- Change in PROMIS-CAT score in Fatigue (4 questions)
 - Measurement: self-reported measure of fatigue
 - Range: 0-100 (higher values indicate more fatigue)
- Change in PROMIS-CAT score in Pain interference (4 questions)
 - Measurement: self-reported measure of pain interference
 - Range: 0-100 (higher values indicate more interference)
- Change in PROMIS-CAT score in Pain intensity (1 question)
 - Measurement: self-reported measure of pain intensity
 - Range: 0-10 (higher values indicate more severe pain)
- Change in PROMIS-CAT score in Physical function (4 questions)
 - Measurement: self-reported measure of physical function
 - Range: 0-100 (higher values indicate better physical function)
- Change in PROMIS-CAT score in Sleep disturbance (4 questions)
 - Measurement: self-reported measure of sleep disturbance
 - Range: 0-100 (higher values indicate more sleep disturbance)
- Change in PROMIS-CAT score in Cognitive function (12 questions)
 - Measurement: self-reported measure of cognitive abilities
 - Range: 0-100 (higher values indicate better cognitive abilities)

The timing and modality of outcome measurements is shown in **Table 5**.

Baseline functional assessments with physical therapy staff from Hebrew SeniorLife's outpatient clinic and at the conclusion of the prehabilitation program (before surgery) will be in-person assessments (though some baseline functional assessments may be done

virtually via Zoom). In-hospital outcomes will be assessed via in-person interview or review of medical records. Postoperative assessment on post-op day 30±7 and 90±7 will be conducted via telephone interview, email survey, or medical record review.

Table 5. Timing of outcome measurement. Day 0 is defined as the date of surgery.

Outcome	Baseline functional assessment (In-person or may be done virtually)	Before surgery (In-person)	Hospitalization (In-person / medical record)	Postop Day 30±7 (Telephone / e-mail survey / medical record)	Postop Day 90±7 (Telephone / e-mail survey / medical record)
Feasibility		X			
Change in chair stands	X	X	X (if not done)*		
Change in handgrip strength	X	X	X (if not done)*		
Change in protein intake	X	X	X (if not done)*		
Adherence to exercise		X	X (if not done)*		
Adherence to protein intake		X	X (if not done)*		
Adherence to meditation		X	X (if not done)*		
Adverse events		X	X (if not done)*		
3-D CAM			X		
PQRS			X		
Surgical complications			X		
Length of stay			X		
Readmission				X	X
Death				X	X
PROMIS-CAT scores	X	X		X	X

Abbreviations: CAM, Confusion Assessment Method; PQRS, Postoperative Quality of Recovery Scale; PROMIS-CAT, Patient-Reported Outcomes Measurement Information System-Computer Assessment Test.

* We will try to measure these outcomes before surgery near the conclusion of the prehabilitation program; if not measured before surgery, we will measure them during the hospitalization.

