6.1 Baseline Assessment

Once informed e-consent or remote consent is signed, trained research personnel will administer additional measurements that are not collected as part of preoperative assessment. These measurements (provided below) may be conducted 1) during the telephone call during which informed consent is obtained; 2) during a separate call (if

requested by the patient or caregiver); 3) email survey; 4) during an in-person physical therapy session (for gait speed, chair stands, and handgrip strength); or 5) a combination of these modalities.

- Usual walking speed from 4-meter walk (if not already measured)
- Time to complete 5 chair stands (if not already measured)
- Dominant handgrip strength: average of 3 measurements (if not already measured)
- 3-day diet recall (done by telephone)
- PROMIS Profile CAT v1.0 is a 29-item, computer adaptive, patient-reported outcome measure of social roles/activities, anxiety, depression, fatigue, pain interference/intensity, physical function, and sleep disturbance domains (may be done by telephone or email)
- PROMIS v2.0 Cognition CAT is a 12-item, computer adaptive, patient-reported outcome measure of cognitive function domain (may be done by telephone)

PROMIS (available at <https://www.healthmeasures.net/index.php>) is a publicly available, validated system of highly reliable, precise measures of patient-reported health status for physical, mental, and social well-being for general population as well as people with chronic conditions. It is designed to enhance communications between clinicians and patients in diverse clinical and research settings. Computer adaptive test (CAT) allows accurate assessment with a limited number of questions from the PROMIS item bank, thereby reducing participant burden.

6.2 Medical Record Review:

Trained research personnel will obtain the following data from the OMR and record them in REDCap database:

- Demographic information: age, sex, race, ethnicity
- Chronic comorbidities
- Self-reported functional status: ADL, IADL, physical tasks by Nagi and Rosow-Breslau
- Cognitive function: telephone MOCA
- Physical function: gait speed, dominant handgrip strength, and chair stands
- Nutritional status: height, weight, BMI, weight loss in the past year, serum albumin level

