8.2 Secondary Outcomes

For *secondary outcomes*, we will measure the following:

- Change in 5-chair stand test (time)
 - Measurement: time to complete 5 chair stands (seconds), post-prehabilitation minus pre-prehabilitation
 - Range: -60 to 60 seconds (higher values indicate worsening performance)
- Change in dominant handgrip strength (kg)
 - Measurement: average of 3 measurements of dominant handgrip strength, post-prehabilitation minus pre-prehabilitation
 - Range: -50 to 50 kg (higher values indicate improved performance)
- Change in protein intake (grams)
 - Measurement: 3-day average protein intake from dietary recall, post-prehabilitation minus pre-prehabilitation
 - Range: -100 to 100 grams (higher values indicate greater intake)
- Adherence to exercise
 - Measurement: proportion of days with ≥ 30 minutes of exercise out of 21-28 days per self-report
 - Range: 0-100% (higher values indicate better adherence)
- Adherence to protein intake
 - Measurement: proportion of oral nutritional supplement consumed over the total number of supplements provided per self-report

- Range: 0-100% (higher values indicate better adherence)
- Adherence to meditation
 - Measurement: proportion of days with ≥ 12 minutes of meditation out of 21-28 days per self-report
 - Range: 0-100% (higher values indicate better adherence)
- Adverse events
 - Measurement: proportion of patients who experience any adverse events per self-report
 - Range: 0-100% (higher values indicate more adverse events)

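### Test mode and timing are not fixed for the change in chair stands and handgrip: baseline may be virtual and loosely timed, while the planned pre-surgery test is in person

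*Combined protocol and SAP*

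**What the plan says.** Section 8.2 names two physical performance outcomes as changes across the program: "time to complete 5 chair stands (seconds), post-prehabilitation minus pre-prehabilitation" and "average of 3 measurements of dominant handgrip strength, post-prehabilitation minus pre-prehabilitation". Table 3 also lists both among the measures of feasibility or adherence for the exercise component.

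On mode, the text above Table 5 (Section 8.3) says that functional assessments at baseline and "at the conclusion of the prehabilitation program (before surgery) will be in-person assessments", "though some baseline functional assessments may be done" by Zoom. It does not say which tests or for whom. The baseline column of Table 5 is headed "Baseline functional assessment (In-person or may be done virtually", and the chair stand and handgrip rows are both marked in it. The next column, before surgery, is headed in-person only.

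On baseline timing, Section 6.1 offers several occasions. One is "during an in-person physical therapy session (for gait speed, chair stands, and handgrip strength". It does not say which session, or whether testing comes before that day's exercise. The tests are also conditional, as in "Time to complete 5 chair stands (if not already measured", with the same condition on grip, and no limit is set on the age of an existing value.

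On follow-up timing, the Table 5 footnote says the team will try to test before surgery, and "if not measured before surgery, we will measure them during the hospitalization". It does not restrict this to the time before the operation.

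Section 11 contains no analysis of the change outcomes. No section asks for the same mode at both tests, for mode to be recorded, or for results by mode.

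**The concern.** A change score is interpretable only if both readings are taken in the same way and bracket the program. Here the planned switch of mode can go only from virtual to in person. A systematic mode difference therefore does not average out over participants; it shifts the mean change. All participants receive the program (Section 7), so no control arm shares and cancels the shift.

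Timing adds three separate gaps. A baseline taken after some training would understate the gain. An old existing value would add whatever happened before the program. A follow-up taken after the operation would add the effect of surgery.

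At stake is the reading of two secondary outcomes, in a study that hopes to show its interventions are effective as well as feasible (Section 3) and is meant to inform a larger trial. Virtual baselines may also cluster in participants who train virtually, because Section 7.1 lets preference, technology and transport decide the format of therapy. Mode would then be mixed up with delivery format, which the study also wants to learn about (Section 2).

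**Working it through.** **The plan's own figures.** The plan gives no SD, effect size or precision target for chair stands or grip, so there is nothing to reproduce for these outcomes. Its one derived figure, N = 30 (Section 11.1), concerns the feasibility proportion. At 70% (21 of 30) the exact 95% interval is 0.506 to 0.853, which agrees with the stated lower bound of 0.50. No chair stand or grip input enters it.

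**Mode.** Let δ be the video reading minus the in-person reading for the same performance, and f the share of pairs with a virtual baseline and an in-person follow-up.

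- For such a pair, observed change = post − (pre + δ) = true change − δ.
- Over all pairs, the shift in mean change = −f × δ.
- If video times run long (δ > 0), the result looks like improvement. If they run short, it looks like worsening.

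The documents give neither f nor δ. The size of the shift under assumed values, in seconds:

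| Assumed f | offset 0.5 s | offset 1 s | offset 2 s |
|---|---|---|---|
| 10% | 0.05 | 0.10 | 0.20 |
| 25% | 0.125 | 0.25 | 0.50 |
| 50% | 0.25 | 0.50 | 1.00 |

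No comparable range is offered for grip, because it is unclear whether grip would ever be taken by video.

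**Baseline timing.** The goal is 6 to 8 therapy sessions (Table 3). If baseline is taken at the start of session k of m, the share of supervised sessions already delivered is (k − 1)/m.

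- Session 1: 0%, whichever m applies.
- Session 2: 1/8 = 12.5% to 1/6 = 16.7%.
- Session 3: 2/8 = 25% to 2/6 = 33.3%.

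If gain were linear over sessions (an assumption), these would also be the shares of the gain lost from the change score. The session 2 and 3 rows show what the wording fails to exclude; they are not what the plan states.

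**Existing values and in-hospital follow-up.** Neither can be sized. The first depends on the age of the value. The second depends on how many tests are missed before surgery and on how far the operation itself alters the test.

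**Reach.** The primary outcome counts sessions delivered (Section 8.1). The four progression criteria in Section 12.4 use enrollment per week, sessions delivered, days of self-directed activity and day-90 PROMIS completion. None uses chair stands or grip.

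**The case against.** The best defense is that the plan already means the right thing. Section 8.2 calls the baseline value pre-prehabilitation, and Table 3 speaks of before and after the intervention. Testing at the start of the first therapy session satisfies every section, and a baseline at session 2 or 3 would contradict the outcome definition. This stands as far as intent goes. A reader might infer that the plan takes baselines after training has begun, but the documents do not say so. They only fail to rule it out, because no procedure ties the test to the first session or places it before exercise.

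A reader might also infer that grip will be measured by video. Section 6.1 links grip to a face-to-face session, Section 8.3 says only that some assessments may be virtual, and no section mentions a grip device sent to the home. Video grip rests on the Table 5 column heading alone, and that heading covers other rows as well. The mode point is therefore firm for chair stands and conditional for grip.

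Nor is the in-person pre-surgery test strictly required, since the footnote allows a hospital measurement. That narrows the mode argument to the planned follow-up, but it opens a timing gap of its own.

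Finally, little depends on these outcomes, and a single-arm change would not isolate a program effect even with matched modes. Both statements are true and they limit the severity. They do not remove the point, because the mode shift can arise with the plan followed exactly and cannot be examined later if mode and date were not recorded.

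**Conclusion.** The concern holds in a limited form, and its severity is minor. The plan permits a virtual baseline with a planned in-person follow-up and does not match, record or report mode. A mode difference would enter the change in chair stands in one direction, and the change in grip only if grip is ever taken virtually. Baseline timing is not pinned to the period before training, existing values have no window, and a missed follow-up may fall after the operation.

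Neither the size nor the direction of the resulting bias follows from the documents. The 0.05-1.0 s range for chair stands rests wholly on assumed shares and offsets and is negligible at its lower end. The 12.5-33.3% range rests on linear gain and on late baselines that the plan does not describe. None of these figures should be read as an expected bias. Session delivery as the primary outcome, the sample size and the decision to proceed to a larger trial are untouched.

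**What to change.** In Section 6.1 and Table 5:

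- Require chair stands and grip before any exercise at the first therapy session, or earlier, and state a window within which an existing value may serve as baseline.
- Take grip in person at both visits, and take baseline chair stands in person where possible.
- Record the mode and date of every test, so that in-hospital values can be placed before or after the operation.

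In Section 11, add a short descriptive plan: change for all pairs, and change for same-mode pairs with follow-up before surgery, with mixed-mode and in-hospital values shown separately. Reporting both sets matters because the same-mode subset may differ in transport or access to technology.

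Repeating the test by video for those with a virtual baseline is not recommended. It is not assured that they will have a virtual session to use, and grip would need a home device that the documents do not mention.

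The cost is wording, one or two data fields and a smaller same-mode subset. If all 30 participants had both tests, and in-hospital follow-ups are set aside, virtual baseline shares of 10% to 50% would leave 27 down to 15 same-mode pairs. The sample size and primary outcome do not change.

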- Weekly check-in calls will take place once a week for about 30 minutes per session over 3-4 weeks. During these calls the participant will talk about their goals, discuss personal motivation, and review their progress. They will be asked about any potential adverse events (such as sore muscles or falls).
- A 30 minute telephone interview will take place at the end of the intervention (in weeks 3 or 4). The participant will be asked to provide feedback discussing what parts of the

intervention worked well and what did not. We will use this information for protocol refinement.

The primary outcome is the feasibility of the prehabilitation protocol, defined as the proportion of patients to whom we can deliver an adequate dose ($\geq 50\%$ of the planned sessions) of the 3 core interventions: physical therapy ($\geq 4/8$ sessions), nutrition ($\geq 2/4$ sessions), and meditation ($\geq 2/4$ sessions). Secondary outcomes include 1) adherence to exercise, protein intake and meditation; 2) changes in 5-chair stand time, dominant handgrip strength, patient-centered outcomes, measured using PROMIS scores in physical function, cognitive function, participation in social roles/activities, depression, anxiety, sleep disturbance, pain and fatigue domains at baseline, following completion of the prehabilitation (before surgery), and on postoperative days 30 and 90; 3) clinical outcomes (3-D Confusion Assessment Method,¹ a composite complication score,² length of stay, and 30-day readmission and death); and 4) Postoperative Quality of Recovery Scale³ to be obtained around postoperative day 3; 5) adverse events.

The proposed research will provide necessary information for a larger randomized controlled trial (RCT).

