7. STUDY INTERVENTION

All participants will be enrolled in a prehabilitation program that will start 3-4 weeks prior to the date of scheduled surgery. The intervention will target three principal components (physical activity, nutrition, and meditation) and deliver cognitive behavioral interventions

(Table 3). Each intervention has 1) instructional or training components, delivered by our study team, and 2) self-directed components.

Table 3. Multicomponent prehabilitation program and measures of feasibility and adherence for each component

Target	Intervention	Measures of Feasibility or Adherence
Exercise: Increase muscle function	
 • Physical therapy (home, in-person, hybrid or virtual) 
 • By physical therapists • Average two 1-hour individual sessions per week (delivered in patient's home, in-person center, hybrid, or virtual) • Goal: 6-8 total PT sessions • Endurance, strengthening, flexibility • Self-directed exercise 
 • Goal: 30 mins/day x 4 days per week 	
 • Number of sessions delivered (feasibility) 
 • Number of days with ≥ 30 min exercise per self-report diary • Step count from a wearable activity tracker (Fitbit Fitness tracker): provision of weekly feedback based on step count • Change in 5-chair stands and grip strength pre- and post- intervention
Nutrition: Preserve lean body mass (Patients with CKD will be excluded)	
 • Nutrition counseling 
 • By registered dietitian • Average one 1-hour group session per week • Goal: 3-4 total nutrition education sessions • Self-directed protein consumption 
 • Goal: 1-2 ONS (20 gram)/day x 4 days per week 	
 • Number of sessions delivered (feasibility) 
 • Number of ONS consumed per self-report • Change in protein intake per 3-day dietary recall pre- and post- intervention • Change in quadriceps thickness by ultrasound pre- and post- intervention

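### Chair-stand, handgrip and protein-intake values missed before surgery are to be taken in hospital, and nothing keeps postoperative values out of the change scores or counts the missed assessment as missing

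*Combined protocol and SAP*

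**What the plan says.** Section 8.2 defines three of its seven secondary outcomes as differences across the program:

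- chair stands: "time to complete 5 chair stands (seconds), post-prehabilitation minus pre-prehabilitation"
- grip: "average of 3 measurements of dominant handgrip strength, post-prehabilitation minus pre-prehabilitation"
- protein: "3-day average protein intake from dietary recall, post-prehabilitation minus pre-prehabilitation"

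Table 3 in section 7 describes them in the same way: "Change in 5-chair stands and grip strength pre- and post- intervention" and "Change in protein intake per 3-day dietary recall pre- and post- intervention".

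On timing, the text of section 8.3 before Table 5 says that functional assessments "at the conclusion of the prehabilitation program (before surgery) will be in-person assessments". Table 5 marks all three outcomes at baseline and in the column for the period before surgery. It also marks them, conditionally, in the hospitalization column, and the footnote explains that "if not measured before surgery, we will measure them during the hospitalization".

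Aim 1 (section 3.1) and section 11.1 both plan to estimate how much outcome data is missing. Neither defines missing, and neither mentions values obtained under the footnote.

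**The concern.** The footnote applies only when the pre-surgery value was not obtained, and the patient is then measured in hospital. For a performance test this ordinarily means a patient who has just had a major operation. If that value is used as the post-prehabilitation value, the difference reflects the program, the operation and the hospital stay together. Every participant receives the program, so there is no control group from which the surgical part could be estimated and removed.

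Two results are at stake. The first is the meaning of three secondary outcomes, which Table 3 also lists as measures of feasibility or adherence. The second is the missing-data rate. Whether the end-of-program assessment can be completed before surgery is something this pilot should learn for the later randomized trial. If a late in-hospital value counts as observed, a missed assessment disappears from that rate.

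**Working it through.** **The plan's own figures.** The documents give no expected value, standard deviation or missing rate for the three change scores, so there is nothing of that kind to reproduce. The only relevant figure is N = 30 from section 11.1, used here as a denominator. It is consistent with an exact 95% interval: 21/30 = 70% gives 0.506 to 0.853. The point does not depend on how N was derived.

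**Reading the text.**

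1. The outcome is defined as post- minus pre-prehabilitation (8.2), and the post-program assessment is placed before surgery (8.3 and Table 5).
2. The fallback is triggered by the absence of a pre-surgery value. The outcomes that belong to the hospitalization column outright are delirium on postoperative days 1 to 3, recovery quality on postoperative day 3, complications, and length of stay counted from surgery. The natural reading of the fallback is therefore postoperative. No day or window is set for it.
3. PROMIS scores are also due before surgery, but Table 5 gives them no in-hospital fallback. The three change scores lack that separation.
4. Chair stands and grip reflect the patient's state on the day of testing. A dietary recall reflects the days it covers: one covering only pre-admission days is unaffected whenever it is collected, and one covering later days is not. The documents do not say which days a late recall would cover.
5. The footnote also covers adherence and adverse events. These are self-reports about the program period, so late collection adds recall error but does not change what is measured. They are left out here.

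**Size.** Section 11 names no summary for these outcomes, so a mean is assumed. Let k be the patients measured late, n the patients with a change score, m the mean change without contamination, and D the mean shift caused by surgery and hospital stay in those measured late. Then

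observed mean = m + (k/n) × D.

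The documents give none of k, n or D. The values below are illustrations, not limits or expectations.

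| k | Bias, n = 30 | Bias, n = 24 | Understated missing rate, k/30 | True missing rate if n = 24, (6 + k)/30 |
|---|---|---|---|---|
| 3 | 0.10D | 0.125D | 10 points | 30% |
| 6 | 0.20D | 0.25D | 20 points | 40% |
| 9 | 0.30D | 0.375D | 30 points | 50% |

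The n = 24 columns assume that 6 of 30 patients have no value at all. The reported missing rate would then be 6/30 = 20% in every row.

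To put the formula in units, suppose late values were on average 5 s slower on chair stands. With 6 of 30 late, the mean shifts by 0.20 × 5 = 1.0 s, enough to cancel a true mean improvement of 1 s. The 5 s and the 1 s are assumptions.

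**Direction.** Section 4 names functional decline among the poor surgical outcomes to which frail patients are more prone. Late chair-stand and grip values would therefore tend to mask a benefit. The documents give no direction for protein intake.

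**The case against.** The strongest reply is that the fallback is openly stated and that the plan intends to measure before surgery. Read literally, an in-hospital value is still after prehabilitation. The footnote says only that the value will be measured, not that it will be pooled, and section 11.1 describes no analysis of these change scores and plans no testing. On this view the gap is an unfinished analysis rule. In part that is right: pooling is inferred, and the bias formula assumes a mean that the plan does not name. But the footnote assigns the late measurement to the change outcome itself, and no rule keeps it out, so following the plan as written produces the mixed score.

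Further points stand as limits:

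- The Overview's schedule, "following completion of the prehabilitation (before surgery), and on postoperative days 30 and 90", may belong to the PROMIS scores alone, since Table 5 has no day 30 or 90 entry for chair stands or grip. The conclusion does not need it; section 8.3 is enough.
- Even with perfect timing, a single-arm change score cannot isolate a program effect. That limits how much these outcomes can show, but it is no reason to add the effect of surgery to them.
- Assessment dates may already be captured in the study database; the documents do not show this. Dates alone would not settle which values are analysed.
- The general statement on functional decline is not specific to chair-stand time or grip during the stay, so the direction is likely rather than established.
- Flagging late values and showing results with and without them would also disclose the problem. It would still leave open which result is the defined outcome and how missingness is counted.

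**Conclusion.** The concern holds. Three of the seven secondary outcomes can take in values that do not match their definition, and a reader of the results would have no assured way to see how many. The Aim 1 missing-data rate for these outcomes can also look better than it was.

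No expected size is claimed, because neither the share measured late nor the surgical shift is in the documents. The conclusion rests on two readings: that measurement during the hospitalization ordinarily means after the operation, and that a value collected for a change outcome will be used in it unless a rule says otherwise.

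The reach is limited. The primary outcome has no hospitalization entry in Table 5. The sample size is unaffected, and none of the four progression criteria in section 12.4 uses these change scores. The correction should be made, but it does not threaten the main purpose of the pilot.

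**What to change.** Keep the in-hospital measurement and state how it is used.

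- **Table 5 footnote, add:** *The date of each assessment is recorded. Only chair-stand and handgrip values taken before the operation, and dietary recalls covering only pre-admission days (whenever collected), enter the change scores. Other in-hospital values of these three outcomes are reported separately.*
- **Section 11.1, add:** *For each of these three outcomes, a patient with no such qualifying value counts as missing for that outcome, and the number missed is reported.*

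The cut-offs differ because intake changes on admission, whereas a performance test done in hospital before the operation still precedes the surgical effect.

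The cost is this wording, an assessment-date field if there is none, and fewer change scores. With the same standard deviation and all 30 otherwise measured, excluding 3, 6 or 9 patients multiplies the standard error of the mean change by √(30/27) = 1.054, √(30/24) = 1.118 or √(30/21) = 1.195, that is, about 5%, 12% or 20%. Patients who miss the assessment may differ from the rest, so their number and baseline values should be shown. The sample size, primary outcome and progression criteria stay as they are.
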